7.5. Pharmacokinetics

7.5.1. Blood Sample Collection

Blood samples for pharmacokinetic analysis of GSK2798745 will be collected at the time points indicated in Section [7.1](#) Time and Events Table.

Approximately 2 mL of blood will be collected in EDTA tubes. The actual date and time of each blood sample collection will be recorded. The timing and volume of PK samples may be altered and/or PK samples may be obtained at additional time points to ensure adequate PK monitoring of GSK2798745 and, if possible, any relevant GSK2798745 metabolites.

Where possible, PK monitoring of relevant co-administered drugs and their metabolites will also be undertaken (atorvastatin and simvastatin). Approximately 2 mL of blood will be collected into sodium heparin tubes. The actual date and time of each blood sample collection will be recorded. The volume of such samples may be altered and additional time points may be added to ensure adequate statin PK monitoring.

Additional collection, processing, storage and shipping procedures are provided in the Study Reference Manual (SRM).

7.5.2. Sample Analysis

Plasma analysis will be performed under the control of Platform Technologies and Science-Drug Metabolism and Pharmacokinetics (PTS-DMPK)/ GlaxoSmithKline, the details of which will be included in the Study Reference Manual (SRM). Concentrations of GSK2798745, and co-administered statins and corresponding metabolites (atorvastatin and metabolites, and simvastatin and metabolites) will be determined in plasma samples using the currently approved bioanalytical methodology. Raw data will be archived at the bioanalytical site (detailed in the SRM).

Plasma samples may be analyzed for metabolite M1 dependent upon the availability of an assay. Until this time, GSK will store the remaining plasma from the PK plasma samples for future possible metabolite analysis.

7.6. Biomarker(s)

Blood samples will be taken for NT-proBNP measurement during the Screening Period and at the timepoints indicated in the Time and Event Table, Section 7.1.

Details of sample collection, processing, storage, and shipment requirements are provided in the SRM.

7.7. Genetics

Information regarding genetic research is included in [Appendix 3](#).

8. DATA MANAGEMENT

- For this study subject data will be entered into GSK defined CRFs, transmitted electronically to GSK or designee and combined with data provided from other sources in a validated data system.
- Management of clinical data will be performed in accordance with applicable GSK standards and data cleaning procedures to ensure the integrity of the data, e.g., removing errors and inconsistencies in the data.
- Adverse events and concomitant medications terms will be coded using MedDRA (Medical Dictionary for Regulatory Activities) and an internal validated medication dictionary, GSKDrug.
- CRFs (including queries and audit trails) will be retained by GSK, and copies will be sent to the investigator to maintain as the investigator copy. Subject initials will not be collected or transmitted to GSK according to GSK policy.
- For this study subject data will be collected using GSK defined case report forms and combined with data provided from other sources in a validated data system.
- Management of clinical data will be performed in accordance with applicable GSK standards and data cleaning procedures to ensure the integrity of the data, e.g., removing errors and inconsistencies in the data.
- Adverse events and concomitant medications terms will be coded using MedDRA (Medical Dictionary for Regulatory Activities) and an internal validated medication dictionary, GSKDrug.
- Original CRFs will be retained by GSK, while the investigator will retain a copy. Subject initials will not be collected or transmitted to GSK according to GSK policy.

9. STATISTICAL CONSIDERATIONS AND DATA ANALYSES

This is a double-blind study with the sponsor un-blinded, which allows data to be reviewed on an on-going basis by the sponsor.

9.1. Hypotheses

An estimation approach will be used for the comparison between GSK2798745 treatment and placebo for the change from baseline in DLco at Day 4 and Day 7. Point estimates and associated 95% confidence intervals for the differences in means will be constructed to provide a plausible range of values for the true comparisons of interest.

9.2. Sample Size Considerations

The sample size was determined using an estimation approach in order to provide sufficient precision for the estimation of the DLco comparison between the treatment and placebo groups. A power statement has been calculated to put the sample size in a familiar context.

Based on the DLco measurements reported by [Olsen, 2006], the baseline mean DLco at rest is 15.3 mL/mmHg/min. The within-subject variability (SDw) additionally provided by the Mayo Clinic Investigators is 1.9. The corresponding change from baseline variance (SDw) estimation is 1.5. If we assume the baseline values for HF subjects in the planned study will be similar to the values at rest in the HF group described in this reference, then a 15% increase from baseline would equate to an effect size of 2.3.

In a two-period crossover design (in which a subject receives placebo in one period and an active dose in the other period) with a sample size of 12 subjects, the estimates of the half-widths of the 95% confidence intervals for the difference in the mean change from baseline in DLco (active-placebo) is expected to be approximately 1.36 or less. That is, if the observed difference in the change from baseline for GSK2798745 and placebo is 2.3, then the 95% CI would be (0.94, 3.66).

In addition, 12 subjects would allow the detection of a 2.3 magnitude difference in the mean change from baseline for DLco under assumption that the SDw for change from baseline for DLco is 1.5, using a two-sided t-test with alpha=0.05 with more than 90% power.

9.2.1. Sample Size Assumptions

If a subject is withdrawn from the study prior to completing both study periods, a subject may be enrolled as a replacement so that a total of 12 subjects complete all assessments in the two study period.

9.2.2. Sample Size Sensitivity

If the within-subject standard deviation is higher than expected, the precision of the 95% CI and the power of a two-sided t-test to detect an effect size of 2.3 (mean difference

between the active dose and placebo) with a 5% significance level would be as follows (with a two-period crossover design with 12 subjects):

SDw	Power with Effect Size of 2.3 mL/mmHg/min	Precision of the 95% Confidence Interval
1.9	76%	1.73
2.4	56%	2.2

9.2.3. Sample Size Re-estimation or Adjustment

When 12 subjects have completed both periods, an analysis will be performed to determine whether additional subjects (up to a maximum of 24 subjects) should be enrolled based on the estimate of within-subject variance for the change from baseline in DLco.

9.3. Data Analysis Considerations

9.3.1. Analysis Populations

All Subjects Population

The ‘All Subjects Population’ is defined as all randomized subjects who receive at least one dose of study medication.

Per Protocol Population

The ‘Per Protocol Population’ will consist of any Analysis Population subjects who are compliant with protocol-specific criteria. Subjects with specified protocol deviations will be excluded.

9.3.2. Interim Analysis

Safety, tolerability and efficacy data will be reviewed in-stream by the sponsor. These reviews may include individual subject data, summaries by treatment group and graphical displays. Subjects and all site personnel (except the un-blinded pharmacist) will be blinded to subject randomization. The decision to continue or stop recruitment will be made based on the evaluation of all available safety and efficacy data.

After 12 subjects complete the study, a sample size re-estimation will be performed based on the estimate of within-subject variance for the change from baseline in the DLco measurement. If the within-subject variance for the change from baseline in DLco is assumed reasonable, the study will be considered completed. Otherwise, additional subjects up to a total of 24 may be enrolled into the study. The final analyses and reporting of the study will be performed after all patients have completed the central formal study.

In addition, a Bayesian predictive approach will be used to assess the futility of the percent change from baseline in DLco at Day 7 to help determine whether additional patients are needed after the sample size re-evaluation. However, this alone will not be used as a basis for determining futility.

The futility criteria for the change from baseline in DLco will be based on the predictive probability at the interim that the end of the study difference in the change from baseline in DLco between GSK2798745 treatment and placebo will meet the definition of a positive outcome.

9.4. Key Elements of Analysis Plan

Final analysis will be provided when all subjects have finished the study and the database has been frozen. The construction of analysis data sets will be performed in accordance with all applicable GlaxoSmithKline standards and procedures.

Adjustment for multiplicity of treatment group comparisons and endpoints is not planned. All available data will be used in the analyses as defined in the populations above. Missing values will not be imputed.

9.4.1. Primary Analyses

Profiles for DLco will be summarized and presented graphically by treatment group as appropriate for the data. The change from baseline in DLco at Day 4, Day 5 and Day 7 will be calculated and summarized in tabular format and/or graphically by treatment. For the change from baseline in DLco, a statistical analysis will be performed using a mixed effect model with repeated measures with a fixed effect term for treatment, period and day, with a random effect for subject, day in the repeated statement with subject being subject by period, and baseline as a covariate, if data permit. Point estimates and associated 95% confidence intervals will be constructed for the differences between the active treatment and placebo.

Full details of analysis will be specified in the RAP.

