Primary Analyses	
 Profiles for DLco will be summarized and presented graphically by treatment group and visits as appropriate for the data. The change from baseline in DLco at Day 4, Day 6 and Day 7 will be calculated and summarized in tabular format and/or graphically by treatment. For the change from baseline in DLco, a statistical analysis will be performed using a mixed effect model with repeated measures with a fixed effect term for treatment, period and day, with a random effect for subject, and baseline as a covariate, if data permit. Point estimates and associated 95% confidence intervals will be constructed for the differences between the active treatment and placebo.

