3.4. Statistical Hypotheses

An estimation approach will be used for the comparison between GSK2798745 treatment and placebo for the change from baseline in DLCo at day 4 and day 7. Point estimates and associated 95% confidence intervals for the differences in means will be constructed to provide a plausible range of values for the true comparisons of interest.

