8.1.2. Statistical Model

Analysis of variance (ANOVA) with repeated measure will be performed on DLco. The primary interested outcome is to compare the treatment effects of the two treatments, where the treatment effect is defined as the change of DLco at the end of each treatment period from the corresponding baseline. Methodological differences in how DLco is collected at the two site causes variance differences by site so it will not be possible to pool DLco values across sites.

The model assumes no cross-over effect. This assumption will be tested by the following code:

```
data results;
  set results;
  contrast = 0.5*(baseline_period1 - baseline_period2);
run;

proc ttest alpha=0.10;
  class seq;
  var contrast;
run;
```

Due to the small sample size, this test has a low power to detect cross-over effects, so the assumption will also be tested graphically by looking at a plot of measures overtime. If there are any departures from the distributional assumptions, alternative models will be explored using appropriately transformed data.

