11.13.5. Efficacy Tables

Efficacy Tables					
No.	Population	IDSL / TST ID / Example Shell	Title	Programming Notes	Deliverable [Priority]
DLco					
2.01	Analysis	Non-Standard EFF_T1	Summary Statistics of DLco	DLco has measures on Baseline, Day 4, 5, and 7 for each treatment period and follow-up. Create this table twice, one table with only Mayo patients and another table with only Hennepin patients	IA, SAC [2]
2.02	Analysis	Non-Standard EFF_T2	Summary Statistics of DLco Change from Baseline	Create this table twice, one table with only Mayo patients and another table with only Hennepin patients	IA, SAC [2]
2.03	Analysis	Non-Standard EFF_T12	Summary Statistics of DLco Change from Intervention	Create this table twice, one table with only Mayo patients and another table with only Hennepin patients. This should be the Mean and SD of the Post-Pre difference.	IA, SAC [2]
2.04	Analysis	Non-Standard EFF_T6	Summary of Statistical Analysis Results of DLco	Models should be run with only Mayo patients. Hennepin patients are excluded because of methodological differences.	IA, SAC [2]
Alveolar-capillary Conductance (D_M)					
2.05	Analysis	Non-Standard EFF_T3	Summary Statistics of Gas Transfer Tests	DLno, Dm, Vc, and Dm/Vc have measures on Baseline, Day 4, 5, and 7 for each treatment period and follow-up	SAC [2]
2.06	Analysis	Non-Standard EFF_T2	Summary Statistics of Gas Transfer Tests Change from Baseline	DLno, Dm, Vc, and Dm/Vc have measures on Baseline, Day 4, 5, and 7 for each treatment period and follow-up. Baseline is day -1 for exercise and chronic values, but should be calculated as post minus pre for Saline.	SAC [2]

Efficacy Tables					
No.	Population	IDSL / TST ID / Example Shell	Title	Programming Notes	Deliverable [Priority]
2.07	Analysis	Non-Standard EFF_T12	Summary Statistics of Gas Transfer Tests Change from Intervention	DLno, Dm, Vc, and Dm/Vc have measures on Baseline and Day 5 and 7 for each treatment period. This should be the Mean and SD of the Post-Pre difference.	IA, SAC [2]
Ventilatory Efficiency					
2.08	Analysis	Non-Standard EFF_T7	Summary Statistics of VE/VCO ₂ Ratio	VE/VCO ₂ ratio has measures on Baseline and Day 7 before and after 3-minutes step test. Create this table twice, one table with all patients and another table with Hennepin patients excluded from the statistics.	SAC [2]

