Day 7	B	X	X	XX.X	XX.XX
Follow-up	NA	X	X	XX.X	XX.XX

Example : EFF_T5
Protocol : 201881
Population : Analysis

Page 1 of X

Table 1.05
Summary Statistics of FVC Change from Baseline

Visit	Treatment	N	n	Mean	SD
Day 4	A	X	X	XX.X	XX.XX
Day 7	A	X	X	XX.X	XX.XX
Day 4	B	X	X	XX.X	XX.XX
Day 7	B	X	X	XX.X	XX.XX

Example : EFF_T6
Protocol : 201881
Population : Analysis

Page 1 of X

Table 1.06
Summary of Statistical Analysis Results of DLco

Treatment	Placebo	Adjusted Mean	
		Difference Estimate	95% CI
XX.XX	XX.XX	XX.XX	(XX.XX, XX.XX)

NOTE: Table adjusted accordingly to the study data, with model details added as footnotes.

CONFIDENTIAL

201881

Example : EFF_T7
 Protocol : 201881
 Population : Analysis

Page 1 of X

Table 1.07
 Summary Statistics of Ve/VCO₂ Ratio

Period	Sequence	Treatment	N	Visit	Mean At Rest	SD At Rest	Mean Post 1 Min	SD Post 1 Min	Mean Post 2 Min	SD Post 2 Min	Mean Post 3 Min	SD Post 3 Min	Mean Recovery	SD Recovery
1	AB	A	X	Baseline	XX.X	XX.XX	XX.X	XX.XX	XX.X	XX.XX	XX.X	XX.XX	XX.X	XX.XX
				Day 7	XX.X	XX.XX	XX.X	XX.XX	XX.X	XX.XX	XX.X	XX.XX	XX.X	XX.XX
2	AB	B	X	Baseline	XX.X	XX.XX	XX.X	XX.XX	XX.X	XX.XX	XX.X	XX.XX	XX.X	XX.XX
				Day 7	XX.X	XX.XX	XX.X	XX.XX	XX.X	XX.XX	XX.X	XX.XX	XX.X	XX.XX
Follow-up	AB	NA	X	Follow-up	XX.X	XX.XX	XX.X	XX.XX	XX.X	XX.XX	XX.X	XX.XX	XX.X	XX.XX
1	BA	B	X	Baseline	XX.X	XX.XX	XX.X	XX.XX	XX.X	XX.XX	XX.X	XX.XX	XX.X	XX.XX
				Day 7	XX.X	XX.XX	XX.X	XX.XX	XX.X	XX.XX	XX.X	XX.XX	XX.X	XX.XX
2	BA	A	X	Baseline	XX.X	XX.XX	XX.X	XX.XX	XX.X	XX.XX	XX.X	XX.XX	XX.X	XX.XX
				Day 7	XX.X	XX.XX	XX.X	XX.XX	XX.X	XX.XX	XX.X	XX.XX	XX.X	XX.XX
Follow-up	BA	NA	X	Follow-up	XX.X	XX.XX	XX.X	XX.XX	XX.X	XX.XX	XX.X	XX.XX	XX.X	XX.XX

CONFIDENTIAL

201881

Example : EFF_T8
 Protocol : 201881
 Population : Analysis

Page 1 of X

Table 1.08
 Summary Statistics of Ve/VCO₂ Ratio Change from Baseline

Period	Sequence	Treatment	N	Visit	Mean At Rest	SD At Rest	Mean Post 1 Min	SD Post 1 Min	Mean Post 2 Min	SD Post 2 Min	Mean Post 3 Min	SD Post 3 Min	Mean Recovery	SD Recovery
1	AB	A	X	Day 7	XX.X	XX.XX	XX.X	XX.XX	XX.X	XX.XX	XX.X	XX.XX	XX.X	XX.XX
2	AB	B	X	Day 7	XX.X	XX.XX	XX.X	XX.XX	XX.X	XX.XX	XX.X	XX.XX	XX.X	XX.XX
Follow-up	AB	NA	X	Follow-up	XX.X	XX.XX	XX.X	XX.XX	XX.X	XX.XX	XX.X	XX.XX	XX.X	XX.XX
1	BA	B	X	Day 7	XX.X	XX.XX	XX.X	XX.XX	XX.X	XX.XX	XX.X	XX.XX	XX.X	XX.XX
2	BA	A	X	Day 7	XX.X	XX.XX	XX.X	XX.XX	XX.X	XX.XX	XX.X	XX.XX	XX.X	XX.XX
Follow-up	BA	NA	X	Follow-up	XX.X	XX.XX	XX.X	XX.XX	XX.X	XX.XX	XX.X	XX.XX	XX.X	XX.XX

Example : EFF_T9
 Protocol : 201881

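### The primary DLco model has no treatment-by-day term, so it gives one common difference instead of the promised Day 4 and Day 7 differences and may misstate the Day 7 effect in either direction

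*Protocol*

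**What the plan says.** **Target.** Protocol 9.1 sets the comparison "for the change from baseline in DLco at Day 4 and Day 7", and SAP 3.4 repeats it: "for the change from baseline in DLCo at day 4 and day 7". Both promise point estimates and 95% confidence intervals. SAP 8.1.2 is narrower: "the treatment effect is defined as the change of DLco at the end of each treatment period from the corresponding baseline", which is Day 7. The futility assessment in protocol 9.3.2 is also set at Day 7; its purpose is to "assess the futility of the percent change from baseline in DLco at Day 7".

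**Model.** Protocol 9.4.1 describes a repeated-measures mixed model "with a fixed effect term for treatment, period and day, with a random effect for subject", with day as the repeated factor within subject-by-period and baseline as a covariate. It leaves full details to the SAP. The SAP synopsis gives the same terms: "with a fixed effect term for treatment, period and day, with a random effect for subject, and baseline as a covariate". SAP 8.1.2 names a repeated-measures ANOVA and lists no terms. SAP 3.1 declares no change from the protocol's analysis.

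**Output.** The model results go to Table 2.04, shell EFF_T6 in SAP Appendix 12. It has one value per arm, one adjusted difference and one interval, with no day. Its note reads "Table adjusted accordingly to the study data, with model details added as footnotes".

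**Days.** Protocol 9.4.1 summarises Days 4, 5 and 7. The SAP synopsis says Days 4, 6 and 7. The programming note to Table 2.01 says "DLco has measures on Baseline, Day 4, 5, and 7 for each treatment period and follow-up". No section says which days enter the model.

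**The concern.** A model with only main effects of treatment and day assumes that the active-minus-placebo difference is equal on every day in the model. Its single treatment coefficient is a weighted average over those days. It is neither the Day 4 nor the Day 7 difference unless the two are equal.

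This is an estimation study, so the primary result is the estimate and its interval. If the effect is still building during the week, the common estimate understates Day 7. If the effect fades, it overstates Day 7. The plan never states that a constant effect from Day 4 is assumed. Because the days entering the model are not fixed either, the average has no defined meaning in advance.

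**Working it through.** **1. Inputs from the documents (protocol 9.2).** Effect 2.3 mL/mmHg/min, within-subject SD of change 1.5, 12 completers in a 2×2 crossover, two-sided 5% level. The documents give no effect by day and no between-day correlation, so both are assumed below.

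**2. The plan's own figures.** Half-width = t(0.975, n−2) × SDw × √(2/n), and power comes from the noncentral t with 10 degrees of freedom.

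| SDw | Half-width | Power | Protocol |
|---|---|---|---|
| 1.5 | 2.228 × 1.5 × √(2/12) = 1.36 | 92.2% | 1.36, more than 90% |
| 1.9 | 1.73 | 76.2% | 1.73, 76% |
| 2.4 | 2.18 | 56.3% | 2.2, 56% |

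The planning figures are right. They describe one contrast with one change value per period, which is the precision of a single-day comparison.

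**3. What the main-effects model estimates.** With complete, balanced data the subject effect cancels. Leaving the baseline covariate aside, the treatment coefficient is the sum of w_d × δ_d. Here δ_d is the difference on day d, w = V⁻¹1 / (1′V⁻¹1), and V is the covariance between days within a period. With equal variances across days the weights on Days 4, 5, 7 are:

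- equal correlation: 1/3, 1/3, 1/3
- AR, 0.5 per day: 0.345, 0.241, 0.414
- AR, 0.8 per day: 0.418, 0.124, 0.458
- Days 4 and 7 only: 0.5, 0.5

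**4. Common estimate under assumed day profiles.**

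| Profile on Days 4/5/7 | Three days, in the weight order above | Days 4 and 7 | True Day 7 |
|---|---|---|---|
| Rising 1.15/1.5/2.3 | 1.65, 1.71, 1.72 | 1.73 | 2.3 |
| Proportional to day 1.31/1.64/2.30 | 1.75, 1.80, 1.81 | 1.81 | 2.3 |
| Constant 2.3 | 2.3 | 2.3 | 2.3 |
| Waning 2.3/1.9/1.15 | 1.78, 1.73, 1.72 | 1.73 | 1.15 |

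For example, rising with equal weights is (1.15 + 1.5 + 2.3)/3 = 1.65, which is 0.65/2.3 = 28% below Day 7. Waning with equal weights is (2.3 + 1.9 + 1.15)/3 = 1.78, which is 0.63/1.15 = 55% above.

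These are not bounds, because unequal variances move the weights. With assumed SDs of 1.2, 1.5, 1.9 and AR 0.7 per day the weights become 0.788, 0.030, 0.182. The rising profile then gives 0.788 × 1.15 + 0.030 × 1.5 + 0.182 × 2.3 = 1.37.

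A simulation of the first profile (400 trials, n = 12, SD 1.5, correlation 0.5) agreed. The main-effects estimate was 1.63 with three days and 1.73 with two. The by-day model gave 2.30 and 2.31 for Day 7.

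**5. Precision.** With correlation r between days, the day-averaged half-width is 1.36 × √((1+2r)/3) for three days and 1.36 × √((1+r)/2) for two. For r = 0.3 to 0.7 that is 1.00 to 1.22 and 1.10 to 1.26, against 1.36 for Day 7 alone.

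**The case against.** The strongest reply is that SAP 8.1.2, the section that defines the model, sets the effect at the end of each period. On that reading the single difference in EFF_T6 is a Day 7 contrast and Day 7 is not distorted. This reading is possible, but it does not rescue the plan. Day 4, promised in both documents, would have no modelled contrast, and a Day 7-only analysis would contradict the repeated-measures model with a day term in the SAP synopsis.

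A second reply is that by-day results appear elsewhere: Tables 2.01 and 2.02, Figure 2.07 with means and intervals by arm, Figure 2.42 for change to Day 7, and subject listings. A reader could compute a Day 7 difference from these, which limits the loss. SAP Table 3 assigns formal DLco analysis to tables only, however, and no display is said to give a modelled difference by day. The Figure 2.42 mock-up is not visible, so its exact content cannot be confirmed.

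Three further points stand as qualifications:

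- The day profiles are assumed, and nothing in the documents suggests waning under daily dosing.
- The precision at 12 subjects will probably not be reached. SAP 4.1 says that the prediction was run on 10 subjects and one more would be enrolled, and Table 2.04 uses one site only.
- SAP section 2 removed the exploratory Bayesian analysis, so the futility assessment is weak support for choosing Day 7. The definition in SAP 8.1.2 is enough by itself.

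**Conclusion.** The concern holds as stated. That the listed terms cannot produce separate Day 4 and Day 7 differences follows from the model's structure and needs no assumption. The SAP does not repair this.

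Whether the reported number is biased for Day 7 depends on how the effect develops, which the documents do not say. Under the equal-variance illustrations, the common estimate is 21% to 28% below Day 7 if the effect rises, 50% to 55% above if it wanes, and unbiased with a narrower interval if it is constant. The direction is therefore open. This should be fixed because it concerns the primary estimate, but it does not invalidate the trial.

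**What to change.** - Add a treatment-by-day fixed effect to the model in protocol 9.4.1, the SAP synopsis and SAP 8.1.2. A period-by-day term is optional.
- State which days enter the model, and that they are the pre-challenge values. Replace Day 6 in the SAP synopsis with Day 5.
- Name the Day 7 pre-exercise contrast as primary, as SAP 8.1.2 implies, and report the Day 4 contrast beside it.
- Give EFF_T6 one row per day. Keep the day-averaged difference as supportive.
- If the model cannot be fitted on so few subjects, a Day 7-only crossover model is a workable fallback. Day 4 would then need its own model.

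The cost is one model term, one sentence and one shell. By-day intervals are wider than the day-averaged one, but at n = 12 and SDw 1.5 the Day 7 half-width is the 1.36 already planned. By the same formula it is 2.262 × 1.5 × √(2/11) = 1.45 for 11 subjects, 1.55 for 10 and 1.84 for 8. The single site's number is not given, so these sizes are assumptions. Smaller numbers widen the interval with or without the change.
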